6.4.2 Recording and Reporting of adverse events

Drug Substance: Movantik
Study Number: ESR-15-11000
Tufts IRB #12043
Version: Protocol version #19
Date: September 10, 2018

All reportable new information that occurs in the study will be reported by the investigative team (sponsor) to the IRB as per the IRB's reportable new information policy and to the study sponsor based on the sponsor's reporting requirements that are outlined as follows:

All reportable new information that occurs in the study will be reported by the investigative team (sponsor) to the IRB as per the IRB's reportable new information policy and to the study sponsor based on the sponsor's reporting requirements that are outlined as follows:

The Sponsor is responsible for safety reporting of adverse events or adverse drug reactions that arise during the Study in accordance with the Code of Federal Regulations Title 21, Part 312, section 312.32 and 312.33 to (i) the US Food and Drug Administration (FDA); (ii) any overseeing Institutional Review Boards; and (iii) all Investigators under this IND.

All SAEs have to be reported to AstraZeneca, whether or not considered causally related to the investigational product. All SAEs will be documented by the investigator. The investigator is responsible for informing the IRB and/or the Regulatory Authority of the SAE as per local requirements.

The investigator will notify AstraZeneca (the Company) of all suspected unexpected serious adverse drug reactions (SUSARs) at the same time that the expedited IND safety reports are sent to the FDA.

When reporting to AstraZeneca, a cover page should accompany the MedWatch form indicating the following:

- Investigator Sponsored Study (ISS)
- The investigator IND number assigned by the FDA
- The investigator's name and address
- The trial name/title and AstraZeneca ISS reference number

Investigative site must also indicate, either in the SAE report or the cover page, the causality of events in relation to all study medications and if the SAE is related to disease progression, as determined by the principal investigator.

Send SAE report and accompanying cover page to AstraZeneca by email to AE Mailbox Clinical Trial (TCS) <[contact]> or by fax to [name] (US Fax number). Email is the preferred method.

Serious adverse events that do not require expedited reporting to the FDA need to be reported to AstraZeneca preferably using the MedDRA coding language for serious adverse events at least <<on a monthly basis>>.

In the case of blinded trials, AstraZeneca will request that the Sponsor either provide a copy of the randomization code/ code break information or unblind those SAEs which require expedited reporting.

Drug Substance: Movantik
Study Number: ESR-15-11000
Tufts IRB #12043
Version: Protocol version #19
Date: September 10, 2018

All SAEs have to be reported to AstraZeneca, whether or not considered causally related to the investigational product. All SAEs will be documented in the study database. The investigator is responsible for informing the IRB and/or the Regulatory Authority of the SAE as per local requirements.

Note: As with any other clinical study, the patient's physician may elect to discontinue the study drug at any time should an adverse effect develop that is felt to be attributable be to study drug administration.

7. BIOLOGICAL SAMPLING PROCEDURES

No biological samples are being collected as part of this study.

8. ETHICAL AND REDULATORY REQUIREMENTS

8.1 Ethical conduct of the study

The study will be performed in accordance with ethical principles that have their origin in the declaration of Helsinki and are consistent with International Conference on Harmonization (ICH)/Good Clinical Practice (GCP), applicable regulatory requirements, and the AstraZeneca policy on Bioethics and Human Biological Samples.

8.2. Subject data protection

The ICF will incorporate wording that complies with relevant data protection and privacy legislation. All subjects will be de-identified using an unique subject number. Confidentiality risks will be minimized given that no PHI or identifying information (other than a subject study code) will be used to identify study subjects. Demographic data for each subject will be maintained in a password-protected computer in [name] locked office. Only Drs. [name], [name], [name] and [name] will engage in data collection for this study and all will be done on the hospital premises. All data entry will be entered on a data collection form on which patient identifying information will be excluded. De-identified data entry into department research computers is password protected. Data will only be reported in aggregate form in any abstract or publication of the study results. All study data will be kept locked in the investigators office. In additional to the investigative team, the Tufts MC IRB, the Medical Gastrointestinal Research Team at AstraZeneca, and the FDA will also have access to this data. Data is not being sent outside of Tufts Medical Center. Only the Tufts Medical Center Investigational Pharmacy will have access to the randomization (allocation) code. The bedside nurse is not a member of the research team (please see Section 9).

8.3 Ethics and regulatory review

The Tufts Medical Center Institutional Review Board (IRB) will approve the final study protocol, including the final version of the ICF. The investigator will ensure the distribution of these documents to the applicable to the IRB and to other members of the investigative team. The opinion of the IRB will be obtained in writing. The investigator will submit this written IRB approval to AstraZeneca or its representative before enrollment of any patient into the study occurs. This study protocol will be re-approved by the IRB annually.

8.4 Changes to the protocol and informed consent form

Drug Substance: Movantik
Study Number: ESR-15-11000
Tufts IRB #12043
Version: Protocol version #19
Date: September 10, 2018

Study procedures will not be changed without the mutual agreement of the PI and AstraZeneca. If there are any substantial changes to the study protocol, then these changes will be documented in a study protocol amendment and where required in a new version of the study protocol. The amendment is to be approved by the IRB. If a protocol amendment requires a change to a center's ICF, AstraZeneca and the IRB are to approve the revised ICF before the revised form is used. If local regulations require, any administrative change will be communicated to or approved by the IRB.

8.5 Audits and inspections

Authorized representatives from a regulatory authority, or the IRB may perform audits or inspections at the center, including source data verification. The purpose of an audit or inspection is to systematically and independently examine all study-related activities and documents, to determine whether these activities were conducted, and data were recorded, analyzed, and accurately reported according to the protocol, GCP, guidelines of the ICH, and any applicable regulatory requirements. The investigator will contact AstraZeneca or its representative immediately if contacted by a regulatory agency about an inspection at the center.

9. STUDY MANAGEMENT

9.1 Study personnel:

Neither the MICU team (ie. physicians) nor the bedside nurse will be part of the research team. As outlined in Table 1, the vast majority of the monitoring that the bedside nurse will be completing for the study will take place within the scope of their regular job duties. The study monitoring that the bedside nurse will be asked to conduct outside of their regular duties will take no more than 10 minutes in total to conduct over a standard 12 hour nursing shift and are all within the scope of practice of an ICU nurse. The MICU team has no specific study-related activities to perform over and above maintaining an awareness that their patient may be in the study and contacting a member of the research team with any questions or concerns.

9.2 Study drug administration

Study medication will be administered by an experienced ICU bedside nurse. The investigative team will be in the ICU each morning to monitor all study procedures over the past 24 hours and is available by pager on a 24/7 basis for any questions that the bedside nurse or any other member of the ICU clinical team may have. The subject's bedside ICU nurse (or his/her designate) will be present in the ICU (and close to the subject's bedside) on a 24-7 basis during entire period of study drug administration.

9.3 Facilities and equipment for managing emergencies

All interventions, tests and procedures will occur while the subject is admitted to an ICU at Tufts MC under the care of the Medical ICU team. Each subject will be monitored on a 24/7 basis by a critical care nurse and a physician member of the ICU team is always in house to respond quickly to any emergencies. A member of the research team will always be available by pager on a 24/7 basis. [name] is a board-certified intensivist who has extensive experience in managing critically ill patients and any potential emergencies that may occur in this population. Drs. [name] and [name] are experienced critical care pharmacists who are used to working with critical care nurses and physicians to identify and help resolve drug-related problems and emergencies in the ICU setting. All critical care nurses at Tufts

Drug Substance: Movantik
 Study Number: ESR-15-11000
 Tufts IRB #12043
 Version: Protocol version #19
 Date: September 10, 2018

Medical Center are well-trained to help identify and resolve with the ICU medical team emergencies that occur in their patients.

9.4 Training of study site personnel

The PI will educate each research team member on their roles and responsibilities. This education and the roles and responsibilities of each research team member will be documented in the study regulatory binder(s). Although neither the Medical ICU team nor bedside nurses will be members of the research team, a member of the investigative team will provide the Medical ICU nurses and physicians an overview of the study protocol and the specific data that will be collected as part of the study.

9.4 Study agreement

An agreement between AstraZeneca and Tufts Medical Center will be in place before any study-related activities take place.

9.5 Study time line and end of study

Protocol Finalization	December, 2016	Month 1
Execution of research agreement	January 2017,	Month 2
IRB approval	January 2017	Month 2
First subject enrolled	May 2017	Month 6
Subject #18 enrolled (50% enrollment)	February 28, 2018	Month 14
Subject #36 enrolled (100% enrollment)	December 31, 2018	Month 23
Publication	March 31, 2019	Month 27

10. DATA MANAGEMENT

All study-related forms (including the original signed ICF) will be kept in a locked investigators office. One copy of the signed ICF will be included in the patient record and another copy will be provided to the patient/legally authorized representative. All study records will be kept for whichever of the following is longest: at least 7 years or for 2 years after the FDA approval of withdrawal of the FDA application.

[name], a senior biostatistician from the Institute for Clinical Research and Health Policy Studies at Tufts Medical Center will work closely with the rest of the research team to provide direction, guidance, and assistance regarding data management and analysis. [name] has worked with our group on prior studies. Drs. [name], [name] and [name] will check all subject case report forms (CRFs) for completeness at the time of data collection. All data collection forms including the CRFs will be stored in a locked cabinet in [name] locked office at all times. Drs. [name] and [name] will conduct all data entry into MS Excel. Both have extensive experience in entering data into MS Excel for other investigations our group has completed. Drs. [name] will monitor the integrity of data entry. Data will be stored in a specified directory on [name] computer, which is password-protected and will be located in his locked office (in a secure building) and backed up regularly.

11. EVALUATION AND CALCULATION OF VARIABLES

Drug Substance: Movantik
Study Number: ESR-15-11000
Tufts IRB #12043
Version: Protocol version #19
Date: September 10, 2018

11.1 Calculation or derivation of efficacy variables

Please see table 1 and study objectives section

11.2 Calculation or derivation of safety variables

Please see table 1 and study objectives section

12. STATISTICAL METHODS AND SAMPLE SIZE DETERMINATION

12.1 Description of analysis sets

All patients will be analyzed in the groups to which they were randomly assigned, according to the intention-to-treat principle.

12.2 Methods of statistical analysis

Baseline characteristics of patients will be compared using standard univariate methods (chi-square test, t-test) to confirm the randomization was successful in achieving comparable groups. To test the primary outcome (incidence of lower GI tract paralysis), given that there may be censoring (i.e., subject may die or withdraw from study before developing lower GI tract paralysis), we will present Kaplan-Meier curves for the naloxegol and placebo groups for the time to first development of lower GI tract paralysis (≥ 3 days without a SBM after study randomization) during the ICU stay up to 10 days and compare the curves using a log-rank test. If all subjects complete the study (e.g., no deaths, no withdrawal or loss-to-follow-up for other reasons), then we will instead compare the proportion of patients that develop lower GI tract paralysis after study randomization during the ICU stay up to 10 days between the naloxegol and placebo groups using a chi-square test. The secondary outcome, time to first SBM will be estimated using a Kaplan Meier time to event analysis and compared between groups using a log-rank test. The secondary outcome of the number of ICU days without a SBM will be compared between the naloxegol and placebo groups using the Poisson regression for count data and adjusting for total number of days in the ICU (up to a maximum of 10) as an offset term in the Poisson model. The secondary outcome of the average daily opioid requirements will be compared between groups using either a student t-test or nonparametric Wilcoxon rank-sum test if the assumptions of the student t-test fail to be met. Length of mechanical ventilation and ICU stay will be reported as medians and interquartile ranges and will be compared using the Wilcoxon Rank Sum Test. For all statistical tests of hypotheses, a two-sided p-value of ≤ 0.05 will be considered as statistically significant. As this is a Phase II proof of concept study a p value of <0.10 may still be worth consideration for future study, however. All statistical analyses will be performed using SPSS 17.0. (SPSS, Chicago, IL) or other comparable commercially available statistical software.

[figure not shown]
12.2.1 Interim analyses

As outlined in the DSMB procedure, planned interim analyses will occur to evaluate safety after the enrollment of 10 subjects and after the enrollment of 20 subjects.

12.2.2 Determination of sample size

Drug Substance: Movantik
 Study Number: ESR-15-11000
 Tufts IRB #12043
 Version: Protocol version #19
 Date: September 10, 2018

For the power analysis, the 4-day estimates of failure to defecate (i.e., failure to have a SBM) from the Kaplan-Meier plot presented in the Guardiola et. al. paper [4] was used as the estimate of lower GI tract paralysis. The figure below shows that the estimate of the percent of patients who failed to defecate (1 minus plotted proportion with defecation) by day 4 was 40% in the Prophylaxis group (i.e., the intervention group) vs. 90% in the non-prophylaxis (Treatment) group (i.e., the control group) (see yellow highlights in figure). We believe the 4-day estimate will be strongly related to the primary outcome of lower GI tract paralysis (≥ 3 days without a SBM).

4 estimated freedom of event (defecation) rates are 90% (Placebo) vs. 40% (Prophylactic treatment), all subjects have complete follow-up, and the analysis is done using the log-rank test to compare survival curves. As sensitivity analysis, the table also shows the power of the study with this sample size under different scenarios. Because this is not the final definitive study to determine efficacy, a less stringent alpha of 0.10 may be justified for this Phase II proof-of-concept study which, if positive, would be followed by a confirmatory study [15]. While we expect most subjects to finish the study (based on the inclusion criteria), we have shown the impact on the power if approximately 20% of subjects do not finish the study. We have also varied the estimated proportion of patients failing to defecate by day 4 (i.e., not having a SBM) in the placebo group from 90% to 70% and in the prophylactic treated group from 40% to 50%.

For this Naloxogol randomized trial, we propose enrolling 36 subjects, 18 per group. The statistical power table below shows this sample size yields over 95% power using an alpha of 0.05 if the true day

Statistical Power of Log-Rank Test with n=18 subjects per group (36 total)

Complete study	ALPHA	Proportion Failing to Defecate at Day 4 (Placebo vs. Prophylactic Treated)				
		90% vs. 40%	90% vs. 50%	80% vs. 40%	80% vs. 50%	70% vs. 40%
100%	0.05	99.8%	98.4%	92.7%	76.0%	76.0%
	0.10	100.0%	99.4%	96.2%	84.9%	84.9%
80%	0.05	99.7%	97.6%	90.8%	72.5%	72.5%
	0.10	99.9%	99.0%	95.1%	82.2%	82.2%

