1. INTRODUCTION

1.1 Background

Among the more than 5 million adults who are admitted to an ICU each year in the USA, most receive IV opioid therapy. Overall, IV opioid use in critically ill adults is increasing given the greater awareness of untreated pain in this population and a recent level 1 recommendation in the Society of Critical Care Medicine's Pain, Agitation and Delirium Practice Guidelines for Critically Ill Adults that an analgesia-first (analgo-sedation) approach be used to optimize patient safety and comfort and improve tolerance with mechanical ventilator support [1]. In critically ill adults with acute respiratory distress syndrome, high-dose infusions of opioids are frequently used to depress respiratory drive and reduce oxygenation needs.

Paralysis of the lower gastrointestinal (GI) tract, defined as the inability to pass stool due to impaired peristalsis, is a common sequelae of opioid use in the critically ill. [2] As outlined in the 2012 recommendation's from the European Society of Intensive Care Medicine's Working Group for Defining Gastrointestinal Function in Intensive Care Patients, paralysis of the lower GI tract, defined as the absence of stool for 3 or more days, in the absence of mechanical GI obstruction, is the preferred terminology for opioid-associated bowel dysfunction rather than constipation given that the symptoms of constipation (e.g., painful defecation, abdominal pain, and a feeling of incomplete bowel evacuation) are not possible to evaluate in most patients in the ICU. Paralysis of the lower GI tract occurs in up to 72% of critically ill adults. [4-7]

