12.2.2 Determination of sample size

For the power analysis, the 4-day estimates of failure to defecate (i.e., failure to have a SBM) from the Kaplan-Meier plot presented in the Guardiola et. al. paper [4] was used as the estimate of lower GI tract paralysis. The figure below shows that the estimate of the percent of patients who failed to defecate (1 minus plotted proportion with defecation) by day 4 was 40% in the Prophylaxis group (i.e., the intervention group) vs. 90% in the non-prophylaxis (Treatment) group (i.e., the control group) (see yellow highlights in figure). We believe the 4-day estimate will be strongly related to the primary outcome of lower GI tract paralysis (≥ 3 days without a SBM).

90% (Placebo) vs. 40% (Prophylactic treatment), all subjects have complete follow-up, and the analysis is done using the log-rank test to compare survival curves. As sensitivity analysis, the table also shows the power of the study with this sample size under different scenarios. Because this is not the final definitive study to determine efficacy, a less stringent alpha of 0.10 may be justified for this Phase II proof-of-concept study which, if positive, would be followed by a confirmatory study [15]. While we expect most subjects to finish the study (based on the inclusion criteria), we have shown the impact on the power if approximately 20% of subjects do not finish the study. We have also varied the estimated proportion of patients failing to defecate by day 4 (i.e., not having a SBM) in the placebo group from 90% to 70% and in the prophylactic treated group from 40% to 50%.

Statistical Power of Log-Rank Test with n=18 subjects per group (36 total)

Complete study	ALPHA	Proportion Failing to Defecate at Day 4 (Placebo vs. Prophylactic Treated)				
		90% vs. 40%	90% vs. 50%	80% vs. 40%	80% vs. 50%	70% vs. 40%
100%	0.05	99.8%	98.4%	92.7%	76.0%	76.0%
	0.10	100.0%	99.4%	96.2%	84.9%	84.9%
80%	0.05	99.7%	97.6%	90.8%	72.5%	72.5%
	0.10	99.9%	99.0%	95.1%	82.2%	82.2%

For this Naloxogol randomized trial, we propose enrolling 36 subjects, 18 per group. The statistical power table below shows this sample size yields over 95% power using an alpha of 0.05 if the true day 4 estimated freedom of event (defecation) rates are

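### The power table does not show what happens near the 72% paralysis rate in section 1.1: its 70% vs 40% column repeats the 80% vs 50% column, the 70% vs 50% corner is missing, and the 90% placebo rate behind the headline is not reconciled with 72%

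*Protocol*

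**What the plan says.** Protocol section 1.1 describes lower GI tract paralysis as "defined as the absence of stool for 3 or more days, in the absence of mechanical GI obstruction" and states: "Paralysis of the lower GI tract occurs in up to 72% of critically ill adults".

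Section 12.2.2, in both protocol and SAP, takes the proportion not defecating by day 4 in a published laxative-prophylaxis study as its estimate of paralysis. That proportion "by day 4 was 40% in the Prophylaxis group (i.e., the intervention group) vs. 90% in the non-prophylaxis (Treatment) group". The link to the trial's endpoint is a stated belief: "We believe the 4-day estimate will be strongly related to the primary outcome of lower GI tract paralysis". The conclusion is that "this sample size yields over 95% power using an alpha of 0.05 if the true day" 4 rates are 90% and 40%, with complete follow-up and a log-rank test.

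As a sensitivity analysis, the section says the failure proportion was varied "in the placebo group from 90% to 70% and in the prophylactic treated group from 40% to 50" per cent. The table has five columns: 90/40, 90/50, 80/40, 80/50 and 70/40. The lowest power printed is 72.5%.

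**The concern.** Three things in 12.2.2 affect how the reader judges 36 patients.

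- **Base case.** The placebo rate of 90% lies above the only general figure the protocol gives for the condition, and neither document says why.
- **Printed 70/40 column.** This is the one column near 72%. Its four entries are exactly those of the 80/50 column. The two scenarios have different hazard ratios and different event counts, so four identical values would be surprising.
- **Missing corner.** Two rates varied over the stated ranges allow a 70% vs 50% case. It is the least favourable one and it is absent.

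The trial is meant to inform the size of later studies. If the lower part of the table is wrong and incomplete, a reader will take the worst-case power to be 72.5% and may give a null result more weight than it deserves.

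**Working it through.** **Inputs.** From 12.2.2: 18 per group, the day-4 failure proportions, alpha 0.05 or 0.10, log-rank test, complete follow-up or about 20% not finishing. From 12.2: two-sided testing and a 10-day horizon. From 1.1: 72%. The documents do not state the model behind the table. The one below is inferred because it reproduces four of the five columns.

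**Model.** The event is the first spontaneous bowel movement (SBM), with a constant hazard in each arm.

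- Daily hazard: λ = −ln(p)/4, where p is the proportion failing by day 4.
- Hazard ratio, treated over placebo: HR = ln(p_t)/ln(p_c).
- Expected events by day 10, complete follow-up: d = 18 × [(1 − p_c^2.5) + (1 − p_t^2.5)].
- Power = Φ(½·√d·ln HR − z), with z = 1.960 (alpha 0.05) or 1.645 (alpha 0.10).
- For the 80% rows, exponential dropout leaves 80% at day 10: g = −ln(0.8)/10, and each arm's event probability becomes λ/(λ+g) × (1 − e^(−10(λ+g))).

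**Step 1: the plan's own headline.** At 90/40, HR = 8.70, d = 20.3 and ln HR = 2.163. Then ½ × √20.3 × 2.163 − 1.960 ≈ 2.92, so power is 99.8%. The table prints 99.8%.

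**Step 2: the whole table.** Rows are in the order 100%/0.05, 100%/0.10, 80%/0.05, 80%/0.10.

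| Placebo vs treated | Printed (%) | Recomputed (%) |
|---|---|---|
| 90 vs 40 | 99.8 / 100.0 / 99.7 / 99.9 | 99.8 / 99.9 / 99.7 / 99.9 |
| 90 vs 50 | 98.4 / 99.4 / 97.6 / 99.0 | 98.4 / 99.3 / 97.6 / 98.9 |
| 80 vs 40 | 92.7 / 96.2 / 90.8 / 95.1 | 93.2 / 96.5 / 91.2 / 95.3 |
| 80 vs 50 | 76.0 / 84.9 / 72.5 / 82.2 | 76.7 / 85.2 / 73.1 / 82.4 |
| 70 vs 40 | 76.0 / 84.9 / 72.5 / 82.2 | 68.5 / 78.7 / 65.1 / 75.9 |
| 70 vs 50 | not shown | 38.8 / 51.2 / 36.2 / 48.4 |

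All 16 cells of the first four columns agree within 1 point. In the 70/40 column the printed values exceed the recomputed ones by 7.5, 6.2, 7.4 and 6.3 points.

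**Step 3: the two cases in question.**

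- 70/40: HR = 2.57, d = 26.8. ½ × √26.8 × 0.944 − 1.960 ≈ 0.48, giving 68.5%.
- 70/50: HR = 1.94, d = 25.4. ½ × √25.4 × 0.664 − 1.960 ≈ −0.29, giving 38.8%.

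A 20,000-replicate log-rank simulation gave 68.1% and 39.0%.

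**Step 4: a placebo rate of 72%.** Complete follow-up. The 72% is treated as a day-4 figure, just as 12.2.2 treats 90%.

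| Placebo vs treated | HR | Events | Alpha 0.05 | Alpha 0.10 |
|---|---|---|---|---|
| 72 vs 40 | 2.79 | 26.3 | 74.8% | 83.7% |
| 72 vs 50 | 2.11 | 24.9 | 46.1% | 58.6% |

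Simulation at alpha 0.05 gave 74.7% and 46.1%. With 80% completing, the alpha 0.05 figures are 71.4% and 43.1%.

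The treated rate matters as much as the placebo rate:

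- Keeping the source's relative reduction, 72 × 40/90 = 32, gives 89.9% at alpha 0.05.
- Keeping the 50-point difference, 72 − 50 = 22, gives 98.0%, but 22% lies outside the treated range the plan considers.

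**Step 5: which endpoint this is.** The event in the model that matches the table is the first SBM, which 12.2 lists as a secondary outcome. The primary analysis is a log-rank test on time to paralysis, or a chi-square test on proportions if everyone completes. Treating the same rates as proportions in the chi-square test (18 per group, alpha 0.05) gives 91.8% at 90/40 and 48.9% at 72/40. The table therefore does not transfer directly to the primary analysis.

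**The case against.** The strongest reply is that the plan contradicts nothing. The over-95% statement is expressly conditional on 90% vs 40%, and lower placebo rates are tabulated. The 72% describes critically ill adults in general, whereas this trial enrols patients on IV opioids, whom section 1.2 treats as high-risk. Section 1.2 also admits that the epidemiology is poorly known. All of this stands. What remains is that 12.2.2 does not make the argument, and the tabulated column that should reassure the reader is the one that does not reproduce.

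A reader might infer that 90% is impossible, because patients without stool at day 4 are a subset of those without stool at day 3. That holds only for the same patients, starting point and estimator. The 90% is a Kaplan-Meier estimate. The 72% reads as an incidence, and if it is a crude proportion, patients who leave early stay in its denominator. The documents do not settle this.

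A reader might also infer a shared source, since both places cite reference [4]. The numbering cannot carry that. In the reference list the laxative-prophylaxis study is number 3, and the delirium study is cited as [13] in 1.1 but [12] in section 2.

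Finally, the text says each rate was varied over a range and does not promise every combination. That is fair, but omitting the worst pair still leaves the printed minimum misleading.

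**Conclusion.** The point holds as a reporting and justification defect in 12.2.2. The 70/40 column appears to be a repeat of 80/50 and overstates power by about 6 to 8 points. The omitted 70/50 corner has power of 38.8% (alpha 0.05) or 51.2% (alpha 0.10) with complete follow-up, and 36.2% or 48.4% with 80% completing, so the printed floor of 72.5% is far too high for the stated range. The gap between 90% and 72% is unexplained.

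It is tempting to go further and say that the trial's true power is about 75%, and that this should replace the headline. The documents do not support that. The 74.8% depends on holding the treated rate at 40% and alpha at 0.05, on applying a general ICU figure to opioid-treated patients, and on time to first SBM as the event. Other readings of the same 72% run from 46.1% (treated 50%) to 89.9% (treated 32%).

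The recomputed figures rest on an inferred model: constant hazards, 10 days, 18 per arm. Its support is the agreement with 16 of the 20 printed cells; the four that disagree are the repeated column.

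**What to change.** In 12.2.2 of both protocol and SAP:

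1. Recompute and correct the 70% vs 40% column. The model above gives 68.5/78.7/65.1/75.9%.
2. Add the 70% vs 50% column (38.8/51.2/36.2/48.4%).
3. Either justify a placebo rate above 72% for opioid-treated ICU patients, or set a 72% case beside 90/40. Show 72/40 (74.8% at alpha 0.05, 83.7% at 0.10), 72/50 (46.1% and 58.6%) and, for the source's relative reduction, 72/32 (89.9% at 0.05).
4. State that, within the table at alpha 0.05, power over 95% is reached only at the 90% placebo rate.
5. State that the table is for the log-rank test on time to first SBM and does not directly give the power of the primary paralysis analysis. Name the model and follow-up length used.

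N stays at 36. The cost is a text and table edit and a less favourable stated power.
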